Through Day 150 of follow-up, AEs occurred at similar frequencies between the mAb (804/968, 83%) vs. the Placebo (402/479, 83.9%) groups. SAEs were reported in 108/968 (11.1%) mAb vs. 81/479 (16.9%) Placebo recipients, and none were considered related to study drug. AESIs related to study drug were reported in 5/968 (0.5%) in nirsevimab vs. 3/484 (0.6%) in Placebo. There were no anaphylaxis or other notable hypersensitivity reactions. In the nirsevimab group, 4 infants experienced rash. One infant experienced one day of petechiae occurring 4 months after nirsevimab, which was not assessed by a health care provider. All 3 AESI infants in the Placebo group had rash.

AEs attributed to ADAs have not been observed in the nirsevimab trials. In the Phase 1 adult trial, ADA occurred at a similar frequency in the mAb and Placebo groups. At the baseline visit, 5/103 (4.9%) mAb vs. 3/34 (8.8%) Placebo recipients had ADA. During post-dose visits, 14/102 (13.7%) mAb vs. 5/33 (15.2%) Placebo recipients had ADA. In the nirsevimab Phase 1b/2a infant trial none had ADA at baseline and only the mAb group had ADA at post baseline (20/71, 28.2%) vs. 0/17 in the Placebo group. Aside from 2 infants with transient positive ADA at day 50, all positive ADAs occurred after the intended coverage duration of 150 days. ADA did not impact safety but lowered the drug exposure between days 150 to 360 in some infants.

The Phase 1 MK-1654 study randomized 152 healthy adults in a 3:1 ratio to MK-1654 (100mg IM, 300mg IM, 300mg IV, 1000mg IV and 3000mg IV) vs. Placebo. The overall safety profile of MK-1654 was similar to that of Placebo. No deaths, SAEs, discontinuations due to AEs, clinically significant laboratory AEs, or dose-dependent pattern of drug-related AEs were reported [Aliprantis 2020].

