- RSM01 – 300 mg IV (Cohort 1)
- RSM01 – 300 mg IM (Cohort 2)
- RSM01 – 1000 mg IV (Cohort 3)
- RSM01 – 3000 mg IV (Cohort 4)
- RSM01 – TBD mg IM (Cohort 5)
- Total RSM01 treatment group
- Placebo IV (Cohorts 1, 3, 4)
- Placebo IM (Cohorts 2, 5)
- Total Placebo treatment group

All data listings will be sorted by cohort, treatment group, and participant number.

Study days are calculated with respect to study intervention administration date as below:

- If the assessment/observation date is on or after study intervention administration date, then Study Day = Assessment/Observation Date – Study Intervention Administration Date + 1.
- Otherwise, Study Day = Assessment/Observation Date – Study Intervention Administration Date.

Baseline will be defined as the last non-missing assessment (including repeated and unscheduled assessments) before study intervention administration, unless otherwise specified. If a patient

was rescreened, data from the rescreening period and not the original screening period will be used in the analyses as applicable.

For summary of safety assessments, if there are repeated measurements at a time point, the first non-missing assessment at that time point will be used in the summary tables.

For ADA-positive participants, the date of the first positive ADA result will be considered as the start date of ADA response.

Time to post-baseline ADA detection (weeks) will be calculated as:

$$\begin{aligned} & (\text{Date of first positive ADA assessment} - \text{Study Intervention Administration} \\ & \quad \text{Date} + 1) / 7 \end{aligned}$$

If the first positive ADA is prior to the start of treatment, the formula is revised to:

$$(\text{Date of first positive ADA assessment} - \text{Study Intervention Administration Date}) / 7$$

Duration of ADA immunogenicity response (weeks) is defined as:

$$(\text{Date of last positive ADA assessment} - \text{date of first positive ADA assessment} + 1) / 7$$

For participants with pre-existing positive, duration will be calculated from administration date of RSM01 rather than from date of first positive assessment.

The methodology and data handling specifications for PK data are detailed in [Section 8](#).

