8.1. Pharmacokinetic Concentrations

Whole blood samples on VAMS and serum samples will be collected for measurement of RSM01 concentrations in capillary blood and venous serum as below:

Dose Escalation Phase:

- At Visit 1 (Day 1), PK blood draw will occur pre-dosing, within 5 minutes (\pm 1 minute) after end of infusion for IV dosing only, and at 8-hours (\pm 0.5 hours) post-dose for both IV and IM doses.
- Visit 2 (Day 2): 24-hours (\pm 1 hours)
- Visit 3 (Day 3): (\pm 0 day)
- Visit 4 (Day 6): (\pm 1 day)
- Visit 5 (Day 8): Days 8-10
- Visit 6 (Day 15): (\pm 3 days)
- Visit 7 (Day 29): Days 29-35
- Visit 8 (Day 61): (\pm 7 days)
- Visit 9 (Day 91): (\pm 7 days)
- Visit 10 (Day 121): (\pm 7 days)
- Visit 11 (Day 151): (\pm 7 days)
- Discontinuation visit

Dose Expansion Phase:

- At Visit 1 (Day 1): pre-dose

- Visit 2 (Day 8): Days 8-10
- Visit 3 (Day 29): Days 29-35
- Visit 4 (Day 91): (\pm 7 days)
- Visit 5 (Day 151): (\pm 7 days)
- Discontinuation visit

Individual capillary blood concentration of RSM01 and time deviation data for PK population will be presented in data listings. Capillary blood concentration data will be summarized by scheduled time point for the PP population using descriptive statistics (non-missing observations (N), arithmetic mean (Mean), standard deviation (SD), coefficient of variation (CV%), median, minimum, maximum, Q1 and Q3. Capillary blood concentration data will also be summarized by ADA status using the PK population.

Descriptive statistics of capillary blood concentration of RSM01 data will be calculated using values with the same precision as the source data and rounded for reporting purposes only. The following conventions will be applied when reporting descriptive statistics of PP PK concentration data:

- Mean, Min, Median, Max, Q1, Q3: 3 significant digits
- SD: 4 significant digits
- CV%: 1 decimal place

Concentrations of RSM01 that are below the lower limit of quantification (BLQ) before the first quantifiable concentration will be treated as zero for descriptive statistics. Below the limit of quantification values after the first quantifiable concentration will be set as missing and excluded for summary statistics.

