Mean (\pm SD) capillary blood concentrations of RSM01 versus scheduled time profiles will be plotted by treatment on both linear and semi-logarithmic scales for PK population. Individual capillary blood concentrations versus actual time profiles will be plotted on both linear and semi-logarithmic scales for the PP population. The ADA status for each subject will be displayed on the individual profiles and for ADA positive participants, the titer results will be plotted on the secondary Y-axis.

The same analyses will be performed for venous serum (exploratory objective).

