9.6.1 Terms and Definitions

The detection of ADA to RSM01 will be performed using a validated immunoassay method with tiered testing of screening, confirmatory, and titration, i.e.:

1. All samples will undergo a screening test.
2. If the screening test is positive for ADA, the sample will undergo a confirmatory test. A sample that has a negative or not reportable (NR) screening result will not undergo further testing.
3. If the confirmatory test is positive, the sample will be analyzed to determine the titer. A titer result can be a quantifiable number or not reportable (“titer not reportable” or “TNR”).

The following terms and definitions will be applied in the immunogenicity analyses.

ADA status of a sample

- Baseline ADA negative sample: Screening or confirmatory test of the last sample before administration of study treatment indicates ADA is not detected.
- Baseline ADA NR sample: Screening or confirmatory test of the last sample before administration of study treatment indicates ADA is not reportable.
- Baseline ADA missing: No baseline sample was available for testing.
- Baseline ADA positive sample: Screening and confirmatory tests of the last sample before administration of study treatment indicates ADA is detected. The numeric titer will be reported unless the titer result is NR, which would be reported as positive TNR.
- Post-baseline ADA negative sample: Screening or confirmatory test of sample taken after administration of study treatment indicates ADA is not detected.

- Post-baseline ADA NR sample: Screening or confirmatory test of sample taken after administration of study treatment indicates ADA is not reportable.
- Post-baseline ADA missing: No post-baseline sample was obtained.
- Post-baseline ADA positive sample: Screening and confirmatory tests of sample taken after administration of study treatment indicates ADA is detected. The numeric titer will be reported unless the titer result is NR, which would be reported as positive TNR.

ADA status of a participant

- Baseline ADA negative participant: A participant with baseline ADA negative sample. A participant with NR or no baseline ADA sample is assumed to be baseline ADA negative.
- Baseline ADA positive participant: A participant with a baseline ADA positive or positive TNR sample.
- Post-baseline ADA positive participant: A participant with at least one post-baseline ADA positive or positive TNR sample. An ADA positive participant will be further classified as follows:

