 - Treatment-emergent positive: Participant had a post-baseline ADA positive or positive TNR sample in a participant with a baseline ADA negative sample OR participant had a post-baseline ADA positive sample that is \geq 8-fold increase above baseline titer in a participant with a baseline ADA positive sample. Note that the baseline sample and at least one post-baseline sample must have reportable titer to assess whether pre-existing immunogenicity was treatment-boosted.
 - Treatment-emergent nonevaluable.
 - Treatment-emergent negative.
- Post-baseline ADA negative participant: A participant with no post-baseline ADA positive or positive TNR sample.
- Any ADA detected: Subjects in Baseline ADA Positive AND/OR Treatment-emergent.
- No ADA Detected: Subjects who are Baseline ADA negative AND either Post-baseline ADA negative OR no valid post-baseline results (excluded from immunogenicity population).

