9.6.3 Potential Association of Immunogenicity with Adverse Events

A summary of AEs showing frequency and percentage of participants with AEs will be produced for the following subgroups:

- Any ADA detected
- No ADA detected

10. Missed Assessments due to COVID-19

All visits or assessments missed due to COVID-19 will be presented in a listing.

11. Interim Analysis

An interim analysis is planned after availability of Cohort 2, Cohort 3, and Cohort 4 Day 30 data.

An interim analysis with a formal Safety report is planned for this study when all participants in each of the Dose Escalation Phase cohorts have completed Day 91. In addition, SDTM datasets will be prepared for interim PK modeling. An Interim Report will be prepared when the results from Day 91 become available. Additional interim analyses may occur prior to the primary analysis to aid in the development of individual and population PK models to predict dose levels in infants and assess covariates.

The purpose of this interim analysis will be a strategic review to inform the broader program and future development plans, including the determination of the potential dose of RSM01 in infants. No decision directly related to this study will be made from the results of this interim analysis. Agreement on the analysis plan, unblinding procedures, specific outputs, method of distribution,

the level of data cleaning and details of whom the results will be provided to will be outlined in a separate unblinding plan (which will be finalized prior to the interim analysis).

Firewalled roles will be involved in the interim analysis to create unblinded datasets and perform analyses. The investigator will remain blinded. The sponsor will review blinded (pooled) safety data by cohort and unblinded aggregated PK data by treatment group (RSM01 vs. placebo) within and across cohorts. The sponsor will be blinded at the participant level throughout the study. An unblinding plan will be prepared to include unblinding details.

12. Changes in the Planned Analysis

Any changes from this statistical analysis plan that are not documented in a formal SAP amendment will be documented in the CSR for this study.

13. Change of Statistical Programming Service Provider

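### The AE-by-ADA table in SAP 9.6.3 uses any-time participant status with no link to ADA onset and pools baseline-positive with treatment-emergent cases, so a true association would be diluted

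*SAP*

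**What the plan says.** SAP 9.6 names three key immunogenicity parameters: incidence and characterization, association with PK, and association with TEAEs. The last is carried out in SAP 9.6.3: "A summary of AEs showing frequency and percentage of participants with AEs will be produced for the following subgroups". The groups are participants with any ADA detected and participants with none.

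- **Who is ADA-positive.** SAP 9.6.1 defines the first group: "Any ADA detected: Subjects in Baseline ADA Positive AND/OR Treatment-emergent". Post-baseline positivity needs little: "A participant with at least one post-baseline ADA positive or positive TNR sample". A baseline-negative participant therefore joins the group through one positive sample at any visit.
- **ADA onset.** SAP Section 4 defines a date: "For ADA-positive participants, the date of the first positive ADA result will be considered as the start date of ADA response". It also defines time to detection and duration. SAP 9.6.3 uses none of these.
- **PK.** SAP 8.1 adds: "Capillary blood concentration data will also be summarized by ADA status using the PK population". SAP 9.6.1 defines the status of a participant and also "ADA status of a sample", and 8.1 does not say which it means. For the individual concentration plots, "for ADA positive participants, the titer results will be plotted on the secondary Y-axis".
- **Listing.** SAP 9.1.1 plans a listing on the possible association of AEs with ADA status. Its contents are not specified.
- **Schedule.** Solicited AEs cover Days 1-7 (SAP 9.1.3). After the pre-dose sample, ADA is sampled at Days 15 (±3), 29, 61, 91, 121 and 151 in Cohorts 1-4, and at Days 29 (29-35), 91 and 151 in Cohort 5. Both schedules include a discontinuation visit (Protocol Tables 2 and 3).

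**The concern.** If antibodies affect tolerability, they can do so only once they are present. The table in 9.6.3 sets a participant's whole AE record against a label that may have been earned at the last visit. Events from before any antibody was detected then sit in the ADA-positive column beside events that could be related to it. Participants whose antibodies predate the dose are a different exposure from those who develop ADA after it, yet they share that column.

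At stake is the reading of one of the SAP's three key immunogenicity parameters: a real association could look weaker than it is, or absent. The secondary endpoint itself, ADA incidence, is not affected.

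**Working it through.** The plan gives no figure for this comparison. Its only design figures, the chances of seeing at least one AE, reproduce: for n = 6, 1 − (1 − 0.2353)^6 = 0.80. They do not bear on this point. The comparator ADA percentages in Protocol 2.6 also reproduce: 5/103 = 4.9% and 14/102 = 13.7%.

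**Step 1: schedule.** The solicited window closes on Day 7. The earliest scheduled post-dose ADA sample is Day 15 − 3 = Day 12 in Cohorts 1-4 and Day 29 in Cohort 5, which holds 24 of the 48 RSM01 participants. Only a discontinuation sample could come sooner. SAP 9.6.3 speaks of AEs without excluding solicited ones, so I take them as included.

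**Step 2: dilution on the rate scale.** The share of Days 1-151 before a first positive at Day d is pre = (d − 1)/151. Assume a constant AE rate, full follow-up and a true rate ratio of 2 from first detection. The apparent ratio is then pre + 2 × (1 − pre).

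| First positive | Share before | Apparent ratio |
|---|---|---|
| Day 15 | 14/151 = 9.3% | 1.91 |
| Day 29 | 28/151 = 18.5% | 1.81 |
| Day 61 | 60/151 = 39.7% | 1.60 |
| Day 91 | 90/151 = 59.6% | 1.40 |
| Day 121 | 120/151 = 79.5% | 1.21 |
| Day 151 | 150/151 = 99.3% | 1.01 |

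With a true ratio of 1, the formula gives pre + (1 − pre) = 1 for every d.

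**Step 3: the statistic actually tabulated.** The table gives percentages of participants. If a proportion p of ADA-negative participants has an AE by Day 151, a participant first positive at Day 91 has probability 1 − (1 − p)^1.404, where 1.404 is the unrounded Day 91 ratio from Step 2. Doubling over the whole period would give 1 − (1 − p)^2.

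| p | Doubled throughout | First positive Day 91 |
|---|---|---|
| 20% | 36.0% (ratio 1.80) | 26.9% (1.34) |
| 50% | 75.0% (1.50) | 62.2% (1.24) |
| 80% | 96.0% (1.20) | 89.6% (1.12) |

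The percentage scale compresses the ratio by itself, and the timing compresses it further.

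**Step 4: group size.** Assume the comparator adult rates apply. The overlap between baseline and post-dose positives is not given.

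- Any ADA: 48 × 14/102 = 6.6 with full overlap, to 48 × 19/102 = 8.9 with none.
- Newly positive: 48 × 9/102 = 4.2 with full overlap, to 6.6 with none.

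**Step 5: PK.** Planned post-dose PK samples that precede the first scheduled post-dose ADA sample are 6 of 12 in the IV cohorts, 5 of 11 in Cohort 2 and 1 of 4 in Cohort 5. For these, only the baseline ADA result exists at the time. A by-visit summary therefore needs a stated rule, and 8.1 gives none.

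**The case against.** The strongest case against is that this is a descriptive table in a trial without hypothesis tests, headed as a potential association. With perhaps 7 to 9 ADA-positive RSM01 participants, case-by-case review may tell more than any table. The SAP already plans sample-level ADA listings, an AE-by-ADA listing, onset and duration dates and profiles with titers, and SAP 9.6.2 reports baseline and treatment-emergent ADA separately. That limits the consequence. It does not correct the table, and the contents of the AE listing are left open.

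Four stronger readings are tempting and are not supported:

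- **That the concentration summary also uses whole-study status.** SAP 8.1 does not say so. Concentrations are otherwise summarized by scheduled time point, and if that carries over, pre- and post-onset visits fall on separate rows. The status shown for each subject on the individual profiles hints at participant level but does not settle it. The finding there is ambiguity.
- **That the protocol expects ADA to appear late.** Protocol 2.6 reports that "all positive ADAs occurred after the intended coverage duration of 150 days" for a comparator antibody in infants, and only apart from two infants with transient positives at day 50. It gives no timing for the comparator adult trial and no expectation for RSM01 in adults.
- **That the table would create a false association.** Under the model above, a null effect with full follow-up stays null. For baseline-positive participants, no post-dose event precedes antibody at all; their problem is pooling.
- **That the remedy is to move all pre-onset events into ADA-negative person-time.** This brings in a new bias, because ADA-negative time would hold the whole solicited window and ADA-positive time none of it. If the AE rate on Days 1-7 is assumed to be 5 times the later rate, the null ratio against never-positive participants becomes 151/(7 × 5 + 144) = 0.84. At 10 times it is 151/(7 × 10 + 144) = 0.71. ADA would look protective.

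First detection is also only the latest possible onset, and Cohort 5 has gaps of about 60 days between ADA samples. Some events before detection may follow undetected antibody.

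**Conclusion.** The point holds for the AE table. SAP 9.6.3 sets no temporal link between AEs and ADA, pools two kinds of ADA-positive participant, and on the scheduled visits counts every solicited AE of a treatment-emergent participant as ADA-positive although it precedes first detection. The consequence is dilution, slight for a first positive at Day 15 or 29 and close to complete by Day 151. The size rests on an assumed constant AE rate, full follow-up and a true doubling; the documents supply none of these, and the actual timing of ADA is unknown. For PK, the conclusion is only that SAP 8.1 must say which ADA status it means. This is a cheap improvement to a descriptive analysis. It is not a fault in a primary or secondary endpoint.

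**What to change.** In SAP 9.6.3:

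1. Keep the ever/never table, with baseline-positive and treatment-emergent participants in separate rows.
2. For treatment-emergent participants, add rows for TEAEs with onset before, and on or after, the ADA start date of Section 4. Add a sensitivity version that starts on the day after the last negative sample.
3. Leave Day 1-7 solicited AEs out of the post-onset comparison, and compare with ADA-negative participants over the same study days, not over all ADA-negative person-time.

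In SAP 8.1, state that the concentration summary by ADA status is by scheduled visit, using the status reached at that visit. For visits before the first post-dose ADA sample, that is the baseline status.

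The cost is SAP wording and modest programming on dates already defined; no new data are needed. The downside is few events and wide uncertainty in the post-onset rows, with about 7 to 9 of 48 RSM01 participants having any ADA if the comparator adult rates apply.
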